### Device Setting changes

- At the start of the study period, insulin delivery settings based on data collected during the run-in period will be made available to the investigator.
  - If the investigator agrees with the new settings, they will be programmed into a subject's study pump.
  - If the investigator does not agree with the recommendations, they may be implemented gradually over a period of time, e.g. 1-2 weeks.
  - If the investigator does not agree with the recommendations and does not wish to implement them gradually, details about the disagreement will be noted on the applicable CRF.
- After approximately 2 weeks of the study period, following a pump upload by subjects at home, new device settings will be made available.
  - If the investigator agrees with the new settings, they will be programmed into a subject's study pump.
  - If the investigator does not agree with the recommendations, the investigator will enter details about the disagreement on the applicable CRF.
- After approximately 3 weeks of the study period, following a pump upload by subjects at home, new device settings will be made available.
  - If the investigator agrees with the new settings, they will be programmed into a subject's study pump.

- If the investigator does not agree with the recommendations, the investigator will enter details about the disagreement on the applicable CRF.
- After approximately 4 weeks of the study period, following a pump upload by subjects at home, new device settings will be made available.
  - If the investigator agrees with the new settings, they will be programmed into a subject's study pump.
  - If the investigator does not agree with the recommendations, the investigator will enter details about the disagreement on the applicable CRF.

**Note:** The following list of reasons for rejecting device settings recommendations will be available to the investigator on the applicable CRF:

1. Device settings recommendations are being rejected in order to extend observation from the last device settings recommendations
2. Device settings recommendations are being rejected, because they are too aggressive, e.g. would cause low glucose
3. Device settings recommendations are being rejected, because they are too conservative, e.g. they would cause high glucose
4. Device settings recommendations are being rejected – Other: (Enter comment)

The table below shows an example of a transition schedule between Auto Mode and Manual Mode; different variations will be provided by the Sponsor to the investigational center. The transitions between Auto Mode and Manual Mode should occur between 7am and 12 Noon.

**Table 2. Example of Manual mode Transitions during the study period - Digital Twin Challenge #1**

Week	Day 1	Day 2	Day 3	Day 4	Day 5	Day 6	Day 7
1	Manual Mode	Auto Mode	Auto Mode	Auto Mode	Auto Mode	Auto Mode	Auto Mode
2	Auto Mode	Auto Mode	Manual Mode	Auto Mode	Auto Mode	Auto Mode	Auto Mode
3	Auto Mode	Auto Mode	Auto Mode	Auto Mode	Manual Mode	Auto Mode	Auto Mode

Week	Day 1	Day 2	Day 3	Day 4	Day 5	Day 6	Day 7
4	Auto Mode	Manual Mode	Auto Mode	Auto Mode	Auto Mode	Auto Mode	Auto Mode
5	Auto Mode	Auto Mode	Auto Mode	Manual Mode	Auto Mode	Auto Mode	Auto Mode

## **Digital Twin Challenge #2: Eating a Meal without Giving an Insulin Bolus**

**Purpose:** The challenge is designed to test the post prandial effect of a subject eating a meal without giving an insulin meal bolus. The purpose of this data collection is also to assist in the development of the Digital twin algorithm.

**Rationale:** During routine diabetes management, patients with diabetes may forget to give insulin for their meal. This challenge helps to collect data on how the Digital Twin algorithm will make insulin delivery recommendations in patients who forget to take insulin with their meal.

### **Run-in Period for Digital Twin Challenge #2**

At the conclusion of the run-in period, insulin delivery recommendations (i.e. insulin carbohydrate ratio, basal rate changes, insulin sensitivity and active insulin time) will be calculated by the cloud-based Digital Twin algorithm based on uploaded CareLink™ data.

### **Run-in Period Study Procedures Based on Therapy at Screening**

- Patients who come in using pump with CGM at Screening will spend a minimum of 30 days using the AHCL system during the run-in period. Device settings may be adjusted as needed
- Patients who are using MDI therapy or pump without CGM (CSII) at Screening will spend at least 2 additional weeks using the AHCL system during the run-in period. Part of the extra time will be used to collect blinded CGM data as a baseline. The rest of the time will be used to allow subjects get used to pump and CGM. Device settings may be adjusted as needed.
- With the AHCL system, the auto basal rate target should be set to 100mg/dL for the duration of the study, unless the investigator considers this setting to be a safety issue for a subject. At the investigator's discretion, the setpoint may be set to 120mg/dL.
- All subjects will purposely withhold insulin at either breakfast or lunch on each day of the run-in period (approximately 23 days)
- Subjects will check their blood glucose at the start of the missed bolus meal as well as 2 hours after the start of the meal; they will give correction insulin as needed. Confirmation of BG is entered on an electronic log
- Subjects will record the calculated CHO on an electronic log, because it is not entered into the Bolus Wizard
- Subjects will be asked to upload their pumps and meters weekly

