### **Cohort A: Insulin Delivery Recommendations Derived from the Digital Twin Algorithm**

The Digital Twin algorithm resides in the Medtronic Data Cloud. By wearing the system during the run-in period, the patient starts to accumulate device data that will be uploaded to CareLink™ after 3 full weeks (22 midnights). The algorithm will then calculate individualized insulin delivery recommendations that will be made available to the investigator.

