### **Study Period for Digital Twin Challenge #2 (at study site selected by Sponsor)**

Following the run-in period, subjects will participate in a study period lasting approximately 5-6 weeks. Subjects will be divided into separate groups:

**Group 1:** Approximately 50% of subjects will purposely withhold insulin for either Breakfast or lunch on each day during weeks 1 through 3. The amount of CHO will be collected on a log, because it is not entered into the Bolus Wizard. Subjects will also check their glucose at the start of the meal as well as 2 hours after the start of the meal and give correction insulin as needed. For the remainder of the study, i.e. weeks 4 and 5, subjects in this group will give standard insulin at all meals.

**Group 2:** Approximately 50% of subjects will give standard insulin at all meals for the duration of the study period. CHO data will be collected directly from subject's data entry into the pump through CareLink™.

Subjects will be instructed to upload the pump and meter at specific time points during the study period. Device settings recommendations will be provided during this study period. Investigators should make every attempt to follow these recommendations, except if they do not agree with the device settings recommendations, based on safety concerns. Investigators may adjust device settings based on safety.

[figure not shown]

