## 6.3.3. Cloud-based Digital Twin Algorithm

### DIGITAL TWIN – AUTOMATIC THERAPY UPDATES

[figure not shown]

The Cloud-based Digital Twin algorithm is a mathematical model of an individual patient, based on the patient's historical data, that is used to compute optimized therapy settings for the patient's closed loop sensor-augmented pump system. It is based on Medtronic's virtual patient model in which a patient's historical information is processed through a series of differential equations to predict a patient's physiological response and to adapt insulin delivery, i.e. individualized HCL parameters and therapy factors, accordingly.

The algorithm resides in the Medtronic Data Cloud platform and communicates directly with the Medtronic Data Cloud. It begins to evaluate patient data as soon as he/she starts wearing the system, a period referred to as imprinting. This initial period lasts for approximately 3 weeks. During this time, the algorithm only identifies patterns in a patient's physiological responses and behaviors, but does not provide any therapy recommendations to the patient. Those patterns are then used to establish a virtual model that closely mimics each patient's physiology and behavior (hence the term "Digital Twin").

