**Therapy at time of Screening: MDI/CSII (no CGM):**
  - Study training and start of blinded CGM
  - Start run-in baseline data collection at home with own therapy (at least 7 days). Data loss may occur if a blinded CGM is worn for longer than 14 days. Sensor wear not recommended for more than 10 days.
  - **Next visit is Visit 2A**
- **Therapy at time of Screening: Pump plus CGM:**
  - Disburse study pump and transmitter (AHCL system)
  - Upload pump and meter
  - Verify CareLink™ credentials, complete registration
  - Provide study and device training
  - Start run-in baseline data collection at home with AHCL system (at least 7 days)
  - Auto Mode activation may occur if subjects were using Auto Mode at Screening (i.e., ok to use automated basal insulin delivery feature only)
  - **Next visit is Visit 3**
- Visit 2A (Office): Therapy at time of Screening: MDI/CSII (no CGM)
  - Return to clinic after blinded CGM data collection
  - Return blinded CGM
  - Disburse study pump and transmitter (AHCL system); use in Manual Mode
  - Upload pump and meter
  - Verify CareLink™ credentials, complete registration
  - Provide study and device training
- Visit 2B (Telephone or Office): **Therapy at time of Screening: MDI/CSII (no CGM)** – Day 1 after visit 2A
  - Review Manual Mode settings
- Visit 2C (Telephone or Office): **Therapy at time of Screening: MDI/CSII (no CGM)** – Day 2 after Visit 2A
  - Review Manual Mode settings
- Visit 2D (Telephone or Office): **Therapy at time of Screening: MDI/CSII (no CGM)** – Day 7 (+3 days) after Visit 2A
  - Review Manual Mode settings
- Visit 3 (Office or Telemedicine) – Auto Mode activation, i.e. automated basal and auto correction
  - Should occur at least 7-14 days after start of wearing AHCL system; 14 days may be preferable for those who were on MDI/CSII (no CGM) at time of screening
- Visit 4 (Telephone or office) – Day 1 after Visit 3

- Visit 5 (Telephone or office) – Day 2 after Visit 3
- Visit 6 (Telephone or office) – Day 3 after Visit 3
- Visit 7 (Telephone or office) – Day 4 after Visit 3
- Visit 8 (Telephone or office) – Day 5 after Visit 3
- Visit 9 (Telephone or office) – Day 6 after Visit 3
  - Upload pump and meter
- Visit 10 (Office or Telemedicine) – Day 14 (+7 days) after Visit 3
  - Upload pump and meter during visit
  - Review CareLink™ Upload
  - Instruct subjects to Upload pump and meter at home on Day 23 or 24 after Visit 3

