## Visit Schedule Details – Cohort A: Digital Twin Challenge #2

### Run-in Period Visits: To be completed in 60 days

- Screening Visit 1 (Office): Consent and Screening
- Visit 2 (Office):
  - **Confirm Eligibility**
  - **Therapy at time of screening: MDI/CSII (no CGM)**
  - Study training and start of blinded CGM
  - Start run-in baseline data collection at home with own therapy (at least 7 days). Data loss may occur if a blinded CGM is worn for longer than 14 days. Sensor wear not recommended for more than 10 days.
  - **Next visit is Visit 2A**

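### Challenge #2 orders an omitted meal bolus on every run-in day and puts that at about 23 days, but the run-in is at least 30 days and no printed text names a 23-day window

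*Protocol*

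**What the plan says.** The instruction appears in the Challenge #2 run-in procedures in the Protocol Synopsis (Section 2), Protocol Section 5 and SAP Section 5: "All subjects will purposely withhold insulin at either breakfast or lunch on each day of the run-in period (approximately 23 days".

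The same list sets the length of the run-in. Subjects who arrive on a pump with CGM "will spend a minimum of 30 days using the AHCL system during the run-in period". Those on MDI or a pump without CGM "will spend at least 2 additional weeks using the AHCL system during the run-in period".

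The Challenge #2 visit schedule (Protocol Section 9.2.1) gives the dates:
- Visit 3 activates Auto Mode with auto correction, at least 7 to 14 days after AHCL wear starts.
- The home upload arranged at Visit 10 is due 23 days or more after Visit 3.
- Visit 11 opens the study period on Day 30 (+7) after Visit 3.

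The run-in is to be finished within 60 days.

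Other places show where a figure of about 23 could come from. Section 5, Cohort A, has device data uploaded "after 3 full weeks (22 midnights" of wear. Section 6.3.3 says of imprinting: "This initial period lasts for approximately 3 weeks". For Challenge #1, the matching Visit 10 step reads: "Instruct subjects to Upload pump and meter at home on Day 23 or 24 after Visit 3".

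**The concern.** This sentence tells people with type 1 diabetes to omit insulin on purpose, and Phase 4 (Table 1) applies it to ages 2 to 13. Its scope is the whole run-in, while its count is shorter than any run-in the plan allows. A site must choose which half to follow, and the printed text gives no start day and no stop day.

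What is at stake is exposure. Days withheld after the home upload add omitted boluses without informing that upload. Days withheld before Visit 3 would come when auto correction is not yet active; at most, automated basal delivery is allowed then, for subjects already using Auto Mode at screening.

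The plan can be precise on this. In the study period, Group 1 withholds "on each day during weeks 1 through 3". The run-in sentence has no such window.

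**Working it through.** **Inputs**
- Printed count: 23 days (Challenge #2 run-in procedures).
- Minimum AHCL time in the run-in: 30 days (same list).
- AHCL start to Visit 3: at least 7 days, the lower end of the stated 7 to 14 (Section 9.2.1).
- Visit 3 to home upload: at least 23 days (Section 9.2.1, Visit 10).
- Visit 3 to Visit 11: 30 to 30 + 7 = 37 days (Section 9.2.1).
- Group 1 withholding in the study period: 3 weeks × 7 = 21 days.

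**1. Where does 23 come from?** Three routes give about 23:
- Visit 3 to the home upload: 23 days at the minimum.
- The algorithm's data window: 22 midnights touch 22 + 1 = 23 calendar days.
- The AHCL minimum less the shortest lead-in to Visit 3: 30 − 7 = 23.

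The first and third count from Visit 3. The second is the data window that ends in an upload. None of the three is a whole run-in. The likely intent is therefore Visit 3 to the home upload.

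**2. The literal scope, on the plan's own minimum.** 30 − 23 = 7 more days; 30 / 23 = 1.30. The word approximately does not cover a gap of 30%.

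**3. Realistic reading: start at Visit 3, continue to Visit 11.**
- Days withheld: 30 to 37.
- Excess over the printed count: 30 − 23 = 7 to 37 − 23 = 14.
- Ratio: 30 / 23 = 1.30 to 37 / 23 = 1.61.

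This takes the upload on Day 23. Since Day 23 is a minimum, each day's delay in the upload moves one day from after it to before it; the total to Visit 11 is unchanged.

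**4. Less likely reading: start with AHCL wear, continue to Visit 11.** At least 7 + 30 = 37 days, of which at least 7 precede auto correction. Ages 2 to 6 join the Cohort A schedule at Visit 3, so this reading does not concern them.

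**5. Totals for Group 1, run-in plus study period.**
- With the printed count: 23 + 21 = 44.
- With Visit 3 to Visit 11: 30 + 21 = 51 to 37 + 21 = 58.
- Ratio: 51 / 44 = 1.16 to 58 / 44 = 1.32.

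**6. Does other printed text settle it?** No. No printed text links the withholding to Visit 3 or to the upload. The Challenge #2 visit list shows an instruction on challenge procedures only at Visit 11, after the run-in has ended.

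**The case against.** The strongest reply is that the number tells sites what to do. Every excess count requires a site to set aside the printed 23. Two of the three routes to that figure start at Visit 3, so an earlier start is unlikely to be intended. This stands, and it narrows the practical question to the 7 to 14 days between the upload and Visit 11.

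The safeguards are also real. Each omitted-bolus meal carries glucose checks at the start and at 2 hours, with correction insulin as needed. Sites contact subjects on Days 1 to 6 after Visit 3, and uploads are weekly. Children aged 2 to 13 may not enter a phase until 10 subjects aged 14 or over have completed the corresponding one and the DMC has reviewed safety data. Withholding before Visit 3 would lack auto correction, but not correction altogether.

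Section 9.1 sends sites to the Visit Details Tables (Section 18.4). Those tables and the visit schedule figures were not available for this review and may name the window.

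A reader might infer two stronger points that the documents do not support:
- **Omitting boluses during the own-therapy week.** For MDI/CSII subjects the schedule has "Start run-in baseline data collection at home with own therapy (at least 7 days" under the run-in heading, and 30 + 14 = 44 days or more could be counted. But the withholding list records carbohydrate on a log because it bypasses the Bolus Wizard, which an MDI subject does not have, and the study pump is handed out only at Visit 2A. This reading is implausible.
- **Inconsistent input to the algorithm.** Whether a site starts at Visit 3 or earlier, and stops at the upload or at Visit 11, every day from Visit 3 to the upload has an omitted bolus. If the first recommendations rest on about the three weeks before the upload, their input is the same in all four cases.

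**Conclusion.** The instruction contradicts itself as printed. Its count matches Visit 3 to the home upload; its scope means at least 30 days, or 30 to 37 days from Visit 3 to Visit 11. The realistic cost is 7 to 14 extra omitted boluses per subject between the upload and Visit 11. A less likely cost is at least 7 omitted-bolus days on AHCL before auto correction is activated.

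These figures assume an upload on Day 23, Visit 11 inside its window, and a site that follows the scope over the number. The conclusion about missing text covers only the printed Protocol and SAP. If the Visit Details Tables define the window, the risk of sites diverging falls, but the sentence would still conflict with its own list.

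Endpoints are descriptive and nothing is powered (Protocol Sections 14.4.1 and 14.7), so no analysis is undermined. This is a minor correction, worth making because it concerns deliberate insulin omission, including in children.

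**What to change.** In the Protocol Synopsis, Protocol Section 5 and SAP Section 5, replace the scope and count with a named window, for example: *each day from Visit 3 (Auto Mode with auto correction active) until the home upload made no sooner than Day 23 after Visit 3 (approximately 23 days); no bolus is withheld before Visit 3 or between that upload and Visit 11.*

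If the Visit Details Tables already define a window, copy that wording instead. If the sponsor and investigators do want withholding to run to Visit 11, the text should say so and give 30 to 37 days.

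The cost is one sentence reworded in three places, with no new data or procedures.

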### **Study Period for Digital Twin Challenge #2 (at study site selected by Sponsor)**

Following the run-in period, subjects will participate in a study period lasting approximately 5-6 weeks. Subjects will be divided into separate groups:

**Group 1:** Approximately 50% of subjects will purposely withhold insulin for either Breakfast or lunch on each day during weeks 1 through 3. The amount of CHO will be collected on a log, because it is not entered into the Bolus Wizard. Subjects will also check their glucose at the start of the meal as well as 2 hours after the start of the meal and give correction insulin as needed. For the remainder of the study, i.e. weeks 4 and 5, subjects in this group will give standard insulin at all meals.

**Group 2:** Approximately 50% of subjects will give standard insulin at all meals for the duration of the study period. CHO data will be collected directly from subject's data entry into the pump through CareLink™.

Subjects will be instructed to upload the pump and meter at specific time points during the study period. Device settings recommendations will be provided during this study period. Investigators should make every attempt to follow these recommendations, except if they do not agree with the device settings recommendations, based on safety concerns. Investigators may adjust device settings based on safety.

[figure not shown]
## Device Setting

- At the start of the study period, insulin delivery settings based on data collected during the run-in period will be made available to the investigator.
  - If the investigator agrees with the new settings, they will be programmed into a subject's study pump.
  - If the investigator does not agree with the recommendations, they may be implemented gradually over a period of time, e.g. 1-2 weeks.
  - If the investigator does not agree with the recommendations and does not wish to implement them gradually, details about the disagreement will be noted on the applicable CRF
- After approximately 2 weeks of the study period, following a pump upload by subjects at home, new device settings will be made available.
  - If the investigator agrees with the new settings, they will be programmed into a subject's study pump.
  - If the investigator does not agree with the recommendations, the investigator will enter details about the disagreement on the applicable CRF.
- After approximately 3 weeks of the study period, following a pump upload by subjects at home, new device settings will be made available.
  - If the investigator agrees with the new settings, they will be programmed into a subject's study pump.
  - If the investigator does not agree with the recommendations, the investigator will enter details about the disagreement on the applicable CRF
- After approximately 4 weeks of the study period, following a pump upload by subjects at home, new device settings will be made available.
  - If the investigator agrees with the new settings, they will be programmed into a subject's study pump.
  - If the investigator does not agree with the recommendations, the investigator will enter details about the disagreement on the applicable CRF.

**Note:** The following list of reasons for rejecting device settings recommendations will be available to the investigator on the applicable CRF:

1. Device settings recommendations are being rejected in order to extend observation from the last device settings recommendations

2. Device settings recommendations are being rejected, because they are too aggressive, e.g. would cause low glucose
3. Device settings recommendations are being rejected, because they are too conservative, e.g. they would cause high glucose
4. Device settings recommendations are being rejected – Other: (Enter comment)

## Cohort C: Meal Time Prediction Algorithm

The meal prediction algorithm will look at pump data collected during the run-in period and uploaded to the Medtronic Data Cloud, in order to determine the timing of meal-time predictions. Subjects will not use the App during the run-in period.

Due to a limitation with regard to the availability of the Medtronic PCL App to subjects under 13 years of age, who rely exclusively on the use of Apple products, i.e., iPhones, an Android phone may be provided for use during the study.

While there are *no specific challenges* for this cohort the following study procedures will be implemented:

